4.5.1 Cytokine Release Syndrome

With ATG infusion, the participant may experience Cytokine Release Syndrome (CRS). The signs and symptoms can span a wide clinical spectrum.

Mild Reactions: For mild (grade 1) reactions per the NCI-CTCAE for CRS, the study medication will be continued. The investigator shall take one or more of the following actions, depending on the type of the reaction:

1. Administer additional doses of antihistamine and acetaminophen.
2. Reduce the rate of infusion by 50% or more.
3. For chills and rigors, meperidine may be considered.

Moderate Reactions: For moderate (grade 2) reactions per the NCI-CTCAE for CRS, the study medication may be interrupted at the investigator's discretion. The investigator shall take the following actions, depending on the type of the reaction:

1. Interrupt infusion if any of the following occurs:
 - a. Oral temperature of $> 40.0^{\circ}\text{C}$
 - b. Symptomatic bronchospasm or pulmonary edema
 - c. Allergy-related edema
 - d. Hypotension
2. When the temperature is $< 38.5^{\circ}\text{C}$ and signs and symptoms improve, restart ATG.
3. Closely monitor the participant with pulse oximetry and a blood pressure monitoring; provide ongoing nursing evaluation until at least 2 hours after the infusion is completed.
4. If necessary, glucocorticoids can be given every 6 hours at a dose of 0.5 mg/kg of methylprednisolone or equivalent.
5. Additional supportive or resuscitative measures (such as the use of epinephrine) may be needed if clinically indicated.

Severe Reactions: For severe (grade 3) reactions or greater per the NCI-CTCAE for CRS, the study medication will be discontinued.

[figure not shown]

Figure 12. Rate Adjustments in Response to Cytokine Release Syndrome

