5.8 Interruption of Enrollment/Trial Cessation

This section lists clinical and laboratory adverse events that will necessitate interruption of enrollment in the trial as a whole. As part of their ongoing safety review, the DSMB will make independent judgments regarding other adverse events requiring trial interruption. In addition, should the study be stopped, the FDA will be informed and the study will not resume until both the DSMB and the FDA are in agreement.

1. Any drug related death or Grade 4 SAE; During this trial, any grade 4 SAE death event will be temporarily considered unexpected and potentially drug-related until the event is reported and reviewed by the FDA and DSMB. In this event, the trial will be interrupted, including dosing of participants already enrolled and enrollment of new participants, until the grade 4 SAE or death event is reviewed by both the FDA and DSMB and both agree to the restart of trial enrollment and study agent administration.
2. Severe adverse event (defined in section 7.3) that is possibly, probably or definitely related to study treatment in any of the first 3 participants, or severe adverse events in the same organ system in any 2 participants with the exception of Grade 3 lymphopenia within the first 30 days of drug treatment. This criterion supersedes all rules below (3-8).
3. Occurrence of anaphylaxis during study treatment in any participant. Anaphylaxis is a serious allergic reaction that is rapid in onset and may cause death. Anaphylaxis is highly likely when any one of the following 3 criteria are fulfilled:
 1. Acute onset of an illness (minutes to several hours) with involvement of the skin, mucosal tissue, or both (e.g., generalized hives, pruritus or flushing, swollen lips-tongue-uvula)

AND AT LEAST ONE OF THE FOLLOWING:

 - i. Respiratory compromise (e.g., dyspnea, wheeze-bronchospasm, stridor, reduced peak expiratory flow (PEF), hypoxemia)
 - ii. Reduced Blood Pressure (BP) or associated symptoms of end-organ dysfunction (e.g., hypotonia [collapse], syncope, incontinence)
 2. Two or more of the following that occur rapidly after exposure to a likely allergen for that person (minutes to several hours):
 1. Involvement of the skin-mucosal tissue (e.g., generalized hives, itch-flush, swollen lips-tongue-uvula)
 2. Respiratory compromise (e.g., dyspnea, wheeze-bronchospasm, stridor, reduced PEF, hypoxemia)
 3. Reduced BP or associated symptoms (e.g., hypotonia [collapse], syncope, incontinence)

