 4. Persistent gastrointestinal symptoms (e.g., crampy abdominal pain, vomiting)

3. Reduced BP after exposure to known allergen for that person (minutes to several hours):
 - i. Infants and children: low systolic BP (age specific) or greater than 30% decrease in systolic BP*
 - ii. Adults: systolic BP of less than 90 mm Hg or greater than 30% decrease from that person's baseline

*Low systolic blood pressure for children is defined as less than 70mmHg from 1 month to 1 year, less than (70 mmHg + [2x age]) from 1 to 10 years, and less than 90 mmHg from 11 to 17 years.

4. Any grade 3 cytokine release syndrome (according to CTCAE criteria) that does not resolve within 72 hours or grade 2 cytokine release syndrome that does not resolve within 48 hours at any time in 2 patients.
5. The occurrence of ALT or AST $\geq 3x$ ULN and bilirubin $> 2x$ ULN at any time in any one of the first 10 participants more than 2 of any ATG treated participant, with the exception of those who have been diagnosed with Gilbert's syndrome prior to randomization and have met the criteria listed in sections 4.5.1, 4.5.2 or 5.6 for this occurrence.
6. Grade 3 hypotension or any urgent care visit and/or hospitalization with or without cytokine release syndrome or anaphylaxis any time in 1 of the first 10 or more than 2 of the total ATG treated participants.
7. Grade 2 thrombocytopenia (i.e. $< 75,000/uL$) at any time in more than 2 of the ATG treated participants.
8. Clinical mononucleosis syndrome in a patient who is EBV seropositive at the time of enrollment, between 5 days and 6 months after the last dose of study drug, or at a later time if designated as probably or possibly related to study drug by the study investigator, in more than 2 patients. The syndrome may include: Grade 2 or above fever, pharyngitis, lymphadenopathy, splenomegaly, or rash, with detectable EBV viral load

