7.7 Adverse Event Reporting and Monitoring

The investigator will grade their severity according to common toxicity criteria or study-specific criteria and will decide of their relation to therapy. Events will be assessed and reported consistent with the ICH Guidelines for Good Clinical Practice, 21 CFR 312.32 for expedited safety reporting, and per the guidance of the DHHS Office for Human Research Protections (OHRP). General descriptions of grading are as follows:

- Grade 1 are mild adverse events requiring no specific medical intervention or asymptomatic laboratory findings
- Grade 2 are moderate adverse events, minimal, local, non-invasive intervention
- Grade 3 are severe and undesirable events, significant symptoms requiring hospitalization or invasive intervention
- Grade 4 are life-threatening or disabling events
- Grade 5 are fatal events (death)

The adverse event case report form for the protocol must be completed for all adverse events assessed as grade 2 or higher and grade 1 and higher for AESIs. The investigator is responsible for regular participant follow-up and for ensuring all adverse events are documented and reported appropriately. For reporting serious adverse events (SAE), in addition to the AE case report form, the site should also complete a MedWatch Form and email/fax to the TNCC *within 24 hours of when the site is notified of the event*. This will be reviewed by the TrialNet Medical Monitor and the DSMB as appropriate. Death must be reported immediately. Event outcome and other follow-up information regarding the treatment and resolution of the event will be obtained and reported when available, if not known at the time the event is initially reported. The follow-up information should

contain sufficient detail to allow for a complete medical assessment of the case and an independent determination of possible causality.

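### Halting rule 4 in section 5.8 allows grade 3 cytokine release syndrome longer to resolve than grade 2, so replacing a grade 2 case with a worse one can remove the trigger

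*Combined protocol and SAP*

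**What the plan says.** Section 5.8 lists events that require enrollment to be interrupted. Three rules bear on CRS.

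- **Rule 4**, whose first limb concerns grade 3 CRS and whose second limb, joined by 'or', concerns the milder grade: "does not resolve within 72 hours or grade 2 cytokine release syndrome that does not resolve within 48 hours at any time in 2 patients".
- **Rule 2**, which takes precedence over rules 3 to 8. One limb covers a related severe event in any of the first 3 participants. The other covers "severe adverse events in the same organ system in any 2 participants with the exception of Grade 3 lymphopenia". It has no condition on how long the event lasts. For the meaning of 'severe' it points to section 7.3, which defines a serious adverse event.
- **Rule 6**, for grade 3 hypotension, hospitalization or an urgent care visit, with or without CRS: "any time in 1 of the first 10 or more than 2 of the total ATG treated participants".

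The protocol ranks the grades elsewhere. Section 7.7 says "Grade 2 are moderate adverse events, minimal, local, non-invasive intervention" and "Grade 3 are severe and undesirable events, significant symptoms requiring hospitalization or invasive intervention". Section 4.5.1 lets study drug be interrupted and restarted for grade 2 CRS, whereas "For severe (grade 3) reactions or greater per the NCI-CTCAE for CRS, the study medication will be discontinued".

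**The concern.** A stopping rule should respond at least as readily to a worse event as to a milder one of the same length and count. Rule 4 does the reverse between 48 and 72 hours: a grade 2 case of that length counts towards the trigger and a grade 3 case does not. The documents give no reason for this order.

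The sentence has a second weakness. The count of two patients may belong to both limbs or only to the grade 2 limb, and this decides whether a single grade 3 case beyond 72 hours interrupts the trial.

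Rule 4 is the only rule in section 5.8 devoted to CRS, an expected infusion reaction, and the trial enrolls children from age 6. If sites and the DSMB read the rule differently, or apply it literally, a pause for review could be missed or called inconsistently.

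**Working it through.** The plan states no figure to reproduce. The check applies each rule, as written, to small sets of cases. It classes each case by its maximum grade and uses 60 h as an example of any duration between 48 and 72 h.

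**Inputs.** Rule 4 gives limits of 72 h (grade 3) and 48 h (grade 2) and a count of 2 patients. Rule 2 gives 2 participants with no duration. Rule 6 gives 1 of the first 10, or more than 2 ATG-treated.

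**Step 1: rule 4 and rule 2.** Two readings of rule 4 are possible.

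- Reading A: at least 2 patients must each meet one of the limbs.
- Reading B: one grade 3 case beyond 72 h is enough, and the grade 2 limb needs 2 patients.

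The last column applies rule 2's two-participant limb with 'severe' taken as grade 3 or higher.

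| Cases | Rule 4, A | Rule 4, B | Rule 2 |
|---|---|---|---|
| Two grade 2, 60 h | met | met | not met |
| Two grade 3, 60 h | not met | not met | met |
| One grade 3 and one grade 2, each 60 h | not met | not met | not met |
| Two grade 3, 80 h | met | met | met |
| One grade 3, 80 h | not met | met | not met |

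The inversion stands under both readings. Among these cases they differ only for the single grade 3 case beyond 72 h.

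**Step 2: rule 2 with 'severe' taken as 'serious'.** Section 7.3 counts inpatient hospitalization as serious. Section 4.1 names grade 3 CRS as a reason for admission after outpatient dosing, and section 7.7 links grade 3 to hospitalization or invasive intervention. Two grade 3 cases would therefore very likely meet rule 2. The mixed pair would meet it only if the grade 2 case were itself serious, for example because that participant was admitted.

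**Step 3: rule 6 after the first 10 participants.** More than 2 ATG-treated participants means at least 3. A pair supplies at most 2, so by itself it does not reach the threshold even if both are hospitalized.

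**Step 4: the comparison that matters.** Start with two grade 2 cases of 60 h after the first 10 participants: rule 4 is met. Make one of them grade 3 and change nothing else. Rule 4 is no longer met, rule 6 is not met, and rule 2's two-participant limb is not met on the grade reading. The situation is worse and the trigger is gone.

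**The case against.** The strongest reply is that rule 2 already does the work. It overrides rule 4, ignores duration, and covers two grade 3 CRS cases if 'severe' means grade 3, and very likely if it means 'serious'. Its 30-day phrase hardly matters for an acute infusion reaction. A reader might infer from rule 4 that enrollment would stay open after two grade 3 cases of 48 to 72 hours. The documents do not support that, and it is not claimed here.

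Other safeguards also count. Rule 6 halts for one hospitalization among the first 10, and rule 2 for one related severe event among the first 3. Section 4.5.1 stops study drug in the affected participant. CRS is reported from grade 1 as an event of special interest, and the DSMB may act on its own judgment. Under reading B, grade 3 is also the stricter limb on patient count, though still the looser on time.

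Most of this stands, and it lowers the practical weight of the point. It does not remove it, for three reasons.

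- Rule 2 does not cover the mixed pair on the grade reading, and covers it on the other only if the grade 2 case is serious.
- Rule 2 is itself unclear, because its term and its cross-reference disagree. The grade reading is not obviously the intended one: it exempts only grade 3 lymphopenia, although section 2.3 reports grade 3 serum sickness in all 6 children of the Stage 2 case series, and the TN19 tables place serum sickness in the same category as CRS.
- If rule 2 does cover any two grade 3 cases, the grade 3 limb of rule 4 adds nothing for two such cases under reading A. The two rules still need to be reconciled.

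**Conclusion.** The point holds within limits. Rule 4 is inconsistent with the protocol's own severity order, and the scope of its two-patient count is unclear. The definite gap is one grade 3 and one grade 2 case, each lasting 48 to 72 hours, after the first 10 participants. By itself this pair meets neither rule 4 nor rule 6, nor rule 2's two-participant limb on the grade reading.

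This rests on classing an event by its maximum grade. If a grade 3 event that falls to grade 2 and persists beyond 48 hours counts under the grade 2 limb, some of these cases would meet rule 4; the text does not say. It also assumes that the grade 2 case is not serious in the sense of section 7.3, and that no other participant's event already counts towards rule 2 or rule 6.

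No probability can be attached. A reader might start from the TN19 monotherapy tables, where CRS occurred in 3 of 10 adults and 11 of the other 19 (29 − 10) participants, 14 of 29 in all, and try to project how often the gap would arise. The documents do not give the share of CRS that is grade 3 and lasts 48 to 72 hours. What they do show points to a low share without excluding a higher one: the TN19 tables list every monotherapy CRS event as non-serious, and CRS in the case series was grade 1. The point merits correction because it concerns a stated safety rule and is cheap to settle, not because a missed halt has been shown to be likely.

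**What to change.** The sponsor and DSMB should revise rule 4 of section 5.8 so that:

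- its two limbs are reconciled with each other and with the severity order in sections 4.5.1 and 7.7;
- it states whether the count of two patients governs one limb or both;
- it states how one grade 3 and one grade 2 case count together, and how an event that changes grade is classed.

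Rule 4 should also be reconciled with rule 2, including whether rule 2 means 'severe' by grade or 'serious' as in section 7.3. The hours and counts are for the sponsor and DSMB to set; none is proposed here.

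The cost is about one sentence in rule 4 and a clarified term in rule 2, with possibly a slightly higher chance of a pause for review.

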3.1.2 Exclusion Criteria

Potential participants must **not** meet any of the following exclusion criteria:

1. Immunodeficiency or clinically significant chronic lymphopenia: (Leukopenia ($< 3,000$ leukocytes / μL), neutropenia ($< 1,500$ neutrophils/ μL), lymphopenia (< 800 lymphocytes/ μL), thrombocytopenia ($< 100,000$ platelets/ μL).
2. Hemoglobin less than 13.5 g/dL for adult men and less than 12 g/dL for adult females and less than 11 g/dL for participants under age 18.

3. Active signs or symptoms of acute or chronic infection at the time of randomization including SARS-Cov-2.
4. Uncontrolled autoimmune thyroid disease and/or celiac disease (participants must be well controlled for the previous 6 months).
5. Evidence of prior or current tuberculosis infection as assessed interferon gamma release assay (QuantiFERON).
6. Currently pregnant or lactating or anticipate getting pregnant within the study period.
7. Require use of other immunosuppressive agents including chronic use of systemic steroids.
8. Evidence of current or past HIV or Hepatitis B or current Hepatitis C infection.
9. Any complicating medical issues or abnormal clinical laboratory results that may interfere with study conduct, or cause increased risk to include pre-existing cardiac disease, COPD, sickle cell disease, neurological disease, or blood count abnormalities.
10. A history of malignancies other than of skin.
11. Evidence of liver dysfunction with AST or ALT outside of the reference range.
12. Evidence of renal dysfunction with creatinine outside of the reference range.
13. Increased bilirubin (total and direct) outside of the normal limit (Participants with documentation of Gilbert's Disease permitted).
14. Vaccination with a live virus within the last 4 weeks.
15. Current or ongoing use of non-insulin pharmaceuticals that affect glycemic control within 7 days of screening.
16. Prior treatment with Teplizumab (either in a previous clinical trial or clinically).
17. Has participated in a clinical trial for diabetes prevention previously and received active study agent within 3 months of randomization.
18. Known allergy to ATG or any product excipient
19. Prior treatment with ATG or known allergy or anaphylactic reaction to rabbit-derived products or to any product excipient
20. Prior adverse reactions to heparin.

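### Liver halting rule 5 leaves its two counts unjoined and ties its Gilbert's exemption to sections with no liver criterion, so the text does not settle whether some combined liver events halt the trial

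*Combined protocol and SAP*

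**What the plan says.** Section 5.8 lists events that oblige the sponsor to interrupt enrolment. If the study is stopped, it restarts only when the DSMB and the FDA both agree.

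- **Trigger of rule 5:** "The occurrence of ALT or AST $\geq 3x$ ULN and bilirubin $> 2x$ ULN at any time".
- **Count in rule 5, running into its exemption:** "any one of the first 10 participants more than 2 of any ATG treated participant, with the exception of those who have been diagnosed".
- **Exemption in rule 5:** participants whose Gilbert's was diagnosed before randomisation and who "have met the criteria listed in sections 4.5.1, 4.5.2 or 5.6 for this occurrence".
- **Rule 6, the next item:** a different event, counted "any time in 1 of the first 10 or more than 2 of the total ATG treated participants".
- **Exclusion criterion 13 (section 3.1.2):** bars "Increased bilirubin (total and direct) outside of the normal limit" but lets in participants with documented Gilbert's, so the exemption can be used in practice.
- **Rule 2:** can halt on severe events in one organ system in two participants, and takes precedence over rules 3 to 8.

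**The concern.** A mandatory halting rule should give the same answer to any two people who apply it to the same data. Rule 5 does not, for two separate reasons: its two counts are not joined, and its exemption relies on criteria that the cited sections do not contain.

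The rule matters to this trial. Section 6.2.1 reports transient liver-test abnormalities in aplastic anaemia patients given ATG, with the cause unclear. Appendix 1 schedules liver tests through follow-up, so qualifying results can be found. A participant with known Gilbert's who has a combined ALT/AST and bilirubin rise may or may not count, although the ALT/AST part of the trigger is not a bilirubin finding.

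**Working it through.** The plan states no operating characteristic for rule 5, so there is no figure to reproduce. The check is mainly of the text, followed by an illustration of whether the connector matters.

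**1. The connector.** Take participants without Gilbert's, with the first 10 read as the first 10 given ATG.

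| Qualifying events on ATG | Joined by *or* | Joined by *and* |
|---|---|---|
| One or two, at least one in the first 10 | halt | no halt |
| Three or more, none in the first 10 | halt | no halt |
| Three or more, at least one in the first 10 | halt | halt |
| One or two, none in the first 10 | no halt | no halt |

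The first two rows are unsettled. The last two are the same either way.

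**2. The population.** The first count refers to participants and the second to ATG-treated participants. If the first 10 are all randomised participants, an event in a placebo participant could count, and only about 10 × 68/101 = 6.7, say 7, of the 10 would be on ATG. If they are the first 10 given ATG, neither statement holds.

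**3. The exemption.** The cited sections compare as follows.

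| Section | Subject | ALT, AST, bilirubin or Gilbert's criterion |
|---|---|---|
| 4.5.1 | Cytokine release syndrome, graded actions | none |
| 4.5.2 | Allergic reactions, graded actions | none |
| 5.6 | Withdrawal from treatment, general reasons | none |

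The flow charts in 4.5.1 and 4.5.2 are not reproduced in the text read here. Their captions concern rate changes for cytokine release and interruption for hypersensitivity. No other section supplies the criteria. Three readings remain:

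- Nobody is exempt, because no liver criterion exists to be met.
- Everyone with previously diagnosed Gilbert's is exempt, because the second condition is treated as empty.
- Only those with Gilbert's who also met a cytokine-release, allergy or withdrawal criterion are exempt. This is the most literal reading, but it has no link to the liver.

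**4. How much the connector could matter.** Inputs: 68 ATG participants (section 3.2); independent events at a per-participant rate *p*; nobody exempt. The documents give no rate, so *p* from 1% to 5% is an assumption.

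- A = P(at least 1 event in 10) = 1 − (1 − p)^10
- B = P(at least 3 events in 68), binomial
- *and* = Σ over x = 1 to 10 of P(x events in 10) × P(at least max(0, 3 − x) events in the other 58)
- *or* = A + B − *and*

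| p | A | B | *or* | *and* | *or*, first 10 randomised (7 on ATG) |
|---|---|---|---|---|---|
| 1% | 9.6% | 3.1% | 11.4% | 1.2% | 9.0% |
| 2% | 18.3% | 15.5% | 27.3% | 6.5% | 23.9% |
| 3% | 26.3% | 33.4% | 44.9% | 14.8% | 41.6% |
| 5% | 40.1% | 66.7% | 73.6% | 33.2% | 71.6% |

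For example, at 2%: 18.3 + 15.5 − 6.5 = 27.3. Results come from unrounded values, so a last digit may differ. The last column assumes that events occur only on ATG. The ratio of *or* to *and* runs from 73.6/33.2 = 2.2 to 11.4/1.2 = 9.5. The choice of first-10 population moves the *or* figure by 2.0 to 3.4 percentage points.

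**The case against.** **The intended connector can be guessed.** Rule 6 uses the same two counts joined by *or*, and that is the likelier intent in rule 5. The missing word may also have been lost when the PDF was converted to text. Both points stand and weaken the first defect. They settle neither who the first 10 are nor the exemption, and a lost word cannot account for the mismatched section references.

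**Other rules reach liver injury.** A reader might infer that rule 5 is the trial's only protection against liver injury. The documents do not support that. Rule 1 covers drug-related deaths and Grade 4 serious events, rule 2 covers severe events in one organ system, and rule 6 covers hospitalisation and urgent care visits. The DSMB may also halt on other events at its own judgment. None of these exempts Gilbert's. They are partial cover, however. A rise seen only in laboratory results need not meet any of the three rules. Rule 2 also takes its meaning of severe from section 7.3, which defines serious. DSMB judgment is provided for events outside the list, whereas the listed ones are meant to compel a halt.

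**The cited sections are not empty.** Sections 4.5.1 and 4.5.2 do contain graded criteria, though for other reactions. So it would be wrong to say that the exemption must cover either nobody or everyone with Gilbert's; the third reading in the working also exists. Section 4.1 similarly sends the reader to 4.5.2 for platelet criteria that appear in 4.4.2, which suggests faulty cross-references rather than a deliberate choice.

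**Few participants may be affected.** A reader might count participants outside the rule from an assumed prevalence of Gilbert's. The documents give no prevalence, the exemption requires a diagnosis before randomisation, and only those who also have the combined event affect a halt. No such count is offered here.

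**Conclusion.** The point holds in a limited form. Rule 5, the only liver-specific halting rule, is incomplete as written in three respects: the connector, the population of the first 10, and the criteria for the Gilbert's exemption. The third is the firmest, because nothing in the documents resolves it and a conversion loss would not explain it.

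Not every case is undetermined. Three events in ATG participants without Gilbert's, at least one of them in the first 10, halt under either connector when the first 10 are read as ATG-treated. The unsettled cases are the first two rows of the connector table, a placebo event among the first 10 randomised, and any qualifying event in a participant with previously diagnosed Gilbert's whose inclusion would change the count.

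The roughly 2-fold to 10-fold difference in halting probability rests on the assumed 1% to 5% event rate, independent events and 68 treated participants. It shows that the wording can matter; it does not forecast how often the rule would fire. The textual defects depend on none of these assumptions.

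**What to change.** The sponsor should amend rule 5 and reconcile it with rules 2 and 6:

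- State the word that joins the two counts.
- State the population for each count, including whether the first 10 are all randomised or only ATG-treated participants.
- Correct the references to 4.5.1, 4.5.2 and 5.6, or write the intended exemption criteria into rule 5 itself.
- Say whether a combined event in a participant with known Gilbert's counts.
- Say how rule 5's count of more than 2 works alongside rule 2's count of two, and whether rule 2 means severe or serious.

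Simply deleting the cross-references is not enough. It would exempt every participant with previously diagnosed Gilbert's without saying that this is intended.

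The choice of thresholds and exemption criteria belongs to the sponsor; none is proposed here. The cost is a one-paragraph protocol amendment. ALT, AST and total and direct bilirubin are already measured under section 5.2, so no new tests are needed.
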